**Interpretation:**

The analysis will be based on women who complete the 12-month postpartum cohort follow up. We will use relative risk ratios performed at a two-sided  $\alpha$  level of 0.05.

Summarize how the results will be interpreted. You can include what level of statistical significance will be used to determine the trial's main conclusion/recommendation. You can also describe how disagreement or coherence between primary and secondary results will be interpreted.

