### The objectives of the study are to:

**AIM 1:** Determine the distribution of women across the PrEP cascade (initiation, continuation and persistence on PrEP) and outcomes (maternal HIV incidence, infant HIV incidence, and adverse events) in a cohort of pregnant and breastfeeding women using quantitative and qualitative approaches

- (1) Determine the distribution of women across the PrEP cascade and outcomes including HIV acquisition (maternal and infant) and adverse events
  1. PrEP initiation: defined PrEP start at any time point in the study
  2. PrEP continuation: defined as return to clinic and PrEP refill within 45 days post initiation
  3. PrEP persistence: defined as reporting taking PrEP in  $\geq 5$  out of last 7 days or  $\geq 25$  out of last 30 days (self-reported), or  $\geq 600$  fmol/punch from DBS TDF-DP (objective report)
- (2) Evaluate key predictors of PrEP initiation, continuation and persistence on PrEP including age, substance use, relationship status and partner's serostatus

**AIM 2:** Evaluate patient and provider-level factors associated with the PrEP cascade using quantitative and qualitative approaches

- (1) Evaluate individual-level factors (including risk perception, substance use, sexual activity, and partner/family/community encouragement) associated with PrEP initiation, continuation and persistence on PrEP
- (2) Evaluate pill and study factors (including PrEP-related side effects, time to participate in study, participant-provider communication) associated with PrEP initiation, continuation, and persistence on PrEP
- (3) Evaluate disease factors (including partner's HIV status, HIV-related stigma) associated with PrEP initiation, continuation, and persistence on PrEP

**AIM 3:** Apply an established mathematical model to simulate the impact of improvement in the PrEP cascade on HIV infections averted (maternal and perinatal)

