## Sample size considerations

The projected sample size for the study is *1200 women enrolled from 1st ANC visit until 12-months postpartum (estimated mean of 18-months follow-up)*. This estimate is based on the following assumptions:

- (1) 60% of women will initiate PrEP during the study period (versus approximately 40% who will not);
- (2) Approximately 75% of women on PrEP will be retained in care at 12-months (defined as not missing >1 study visit among women on PrEP)
- (3) 70% of those retained in care (n=378) will adhere to PrEP during at-risk periods.

A sample size of 1200 women yields 80% power to detect identify a relative risk of 2.0 or greater in key covariates including age (<25 vs. >25 years), pregnancy and relationship status associated with PrEP initiation versus non-initiation. A sample size of 378 women (e.g. 70% of women retained in the study on PrEP will be adherent as measured by TDF-DP measures) yields 80% power to detect relative risks of 2.0 or greater associated with persistence in the cohort. The analysis will be based on women who complete the 12-month postpartum cohort follow up. We will use relative risk ratios performed at a two-sided  $\alpha$  level of 0.05.

## Statistical analysis considerations for AIMS 1 & 2

The primary analysis for *Aim 1* will focus on measuring the distribution of women across the PrEP cascade including: initiation, continuation and persistence. **PrEP initiation** will be based on a woman's uptake of PrEP and allow for stoppage and re-initiation; **PrEP continuation** will be defined as not missing >1 visit among those on PrEP (with separate analyses of PrEP stoppage). For **PrEP persistence** for women on PrEP we will measure both *perfect persistence* (i.e. level of objective persistence throughout pregnancy and breastfeeding periods) as well as "*prevention-effective*" persistence (i.e. persistence during times of sexual activity) in participants through objective and subjective measures to evaluate agreement between the two measures, and the level of under- or over-reporting. Primary persistence analyses will use objective measures (TDF-DP from DBS) taken on all those who enrolled and initiated PrEP; subsidiary analyses will consider (i) other persistence measures and (ii) multiple imputation for missing persistence data.

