### Study measures

**Under Aim 1, we will measure the following primary outcomes in the PrEP cascade defined as PrEP initiation, continuation and persistence over time in the cohort.**

1. **PrEP initiation:** # of women who initiate PrEP over time / total # of women in active cohort = proportion of women who initiate PrEP
2. **PrEP continuation:** # of women on PrEP who return for study visits (do not miss more than 1 visit) / total # of women in active cohort who are prescribed PrEP= proportion of women on PrEP who continue in PrEP study

3. **PrEP persistence:** defined as reporting taking PrEP in  $\geq 5$  out of last 7 days or  $\geq 25$  out of last 30 days (self-reported), or  $\geq 600$  fmol/punch (~7 doses/week) from DBS TDF-DP at 3rd trimester, delivery and 6 weeks postpartum (objective report)

**In addition we will measure secondary outcomes defined as continuation and persistence during periods of sexual risk.** Different levels of PrEP continuation and persistence may be needed depending on sexual risk. Our study will measure both perfect persistence (e.g. level of objective persistence throughout pregnancy and breastfeeding periods) as well as “prevention-effective” persistence among participants. We will measure persistence through objective and subjective measures to evaluate the agreement between the two measures, and the level of under- or over-reporting.

- a. **Use of PrEP will be measured via:** (i) quarterly testing of DBS to test for TDF-DP adapted from previous studies of PrEP objective measures; (ii) self-reported items that we have adapted from previous studies (including 7-day, 30-day and last visit recall questionnaires), (iii) pill counts and (iv) pharmacy refill records.
- b. **Measurement of prevention-effective execution:** Execution refers to PrEP persistence during a time when at-risk sex happens. It is calculated by: number of doses reported or recorded/number of expected doses based on HIV risk and PrEP initiation/discontinuation.
- c. **Prevention-effective continuation:** Prevention-effective continuation describes the duration of PrEP use during periods of HIV risk and references the absolute time of use during pregnancy and breastfeeding periods. We will adapt the methodology from previous PrEP studies including FEM-PrEP in SA to create a semi-ordinal composite persistence score measuring plasma TDF-DP from blood specimens collected from DBS every 3-months.

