#### ***Methods/Approach:***

- (1) Study flow figure (see Continuation Flowcharts)
- (2) Number screened per week and month (target= 18 per week, 72 per month) vs number enrolled
  - a. The projected sample size for the study is 1200 women enrolled until 12-months postpartum (estimated mean of 18-months follow-up).
- (3) Subjects initiating PrEP compared to those who do not
  - a. Estimated that 60% of women (n=720) will initiate PrEP during the study period (versus approximately 40% who will not).
- (4) Continuation and persistence by group
  - a. Assumed that approximately 75% of women on PrEP (n=540) will continue on PrEP at 12-months (defined as not missing >1 study visit among women on PrEP);
  - b. Assumed that 70% of those retained in care (n=378) will adhere to PrEP during at-risk periods.
- (5) Final completion rates
  - a. Compare final number of participants who enroll in study, who initiate PrEP, who are retained in care, and who adhere to PrEP to sample sizes needed to yield 80% power (i.e., n=1200, 720, 540, 378, respectively).
- (6) Number of subjects in analysis data sets
  - a. Consider number of participants that will potentially be excluded from analyses because of withdrawal from study, missing data on key covariates or outcomes, etc.

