#### **Methods/Approach:**

- (1) **Primary outcome:** See **Table 1** for precise definitions of (1) PrEP initiation, (2) PrEP continuation, (3) PrEP persistence-subjective, and (4) PrEP persistence-objective
- (2) **Primary analysis:** Describe each outcome listed above via cumulative incidences at fixed intervals (e.g., cumulative PrEP initiation by delivery) and incidence densities over time. The general statistical approaches to these outcomes are analogous; data will be described graphically, including product-limit graphs, with preliminary analyses based on standard approaches for rates and proportions.
  - a. **PrEP initiation** will be modelled using a probit model (preferred to estimate risk factors for common outcomes) with individual-level covariates as fixed effects.
  - b. **PrEP continuation** will be examined using similar approaches; in addition, we will use time-to-event methods to estimate factors associated with time to loss (non-continuation) among women having initiated PrEP.
  - c. **PrEP persistence** will be modelled using mixed effects probit models as above and generalized estimating equations to examine the marginal effect of individual-level covariates on persistence during the study.
    - a. **Sub-group analysis:** we will analyze the primary outcomes by sub-groups including age (<25 and  $\geq$ 25 years), STI diagnosis, relationship status, pregnant/postpartum

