#### **Missing data:**

Primary persistence analyses will use objective measures (TDF-DP from DBS) taken on all those who enrolled and initiated PrEP; subsidiary analyses will consider (i) other persistence measures and (ii) multiple imputation for missing persistence data. Specify any sensitivity analyses. Specify how the impact of missing data on the primary results will be interpreted.

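### The rule restricting the analysis to women who complete follow-up conflicts with the all-initiator populations elsewhere, and the active cohort is undefined, so the denominator of the headline continuation proportion is not fixed

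*Combined protocol and SAP*

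**What the plan says.** The completer sentence, "The analysis will be based on women who complete the 12-month postpartum cohort follow up", appears three times: in Protocol section 6 (Sample size considerations), in the SAP sample size text, and in SAP 2.4 under Interpretation. No outcome is exempted. Each time, the next sentence names relative risks at two-sided alpha 0.05.

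Other current text sets different populations:

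- **Persistence (SAP 2.4, Missing data):** "Primary persistence analyses will use objective measures (TDF-DP from DBS) taken on all those who enrolled and initiated PrEP". The main statistical text of the protocol (for adherence) and of the SAP says the same.
- **Time to non-continuation (SAP 2.4, Methods):** "time-to-event methods to estimate factors associated with time to loss (non-continuation) among women having initiated PrEP".
- **Primary description (SAP 2.4, Methods, item 2):** cumulative incidence at fixed intervals with product-limit graphs, with no completer restriction.
- **Results shell (SAP section 4, Table 2):** continuation at visits 3 to 7 among women on PrEP, again with no completer restriction.
- **Tabulated continuation proportion (Protocol Table 2; SAP Study measures and Table 1):** the denominator is "total # of women in active cohort who are prescribed PrEP". Initiation also uses the active cohort. Neither document defines it.

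The planning counts in SAP 2.2 assume that "approximately 75% of women on PrEP (n=540) will continue on PrEP at 12-months", out of 720 initiators.

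Continuation has two definitions. The Aim 1 objectives use "defined as return to clinic and PrEP refill within 45 days post initiation"; the SAP analysis text and Table 1 use not missing more than one visit. Loss to follow-up also has two rules: more than 8 weeks (Protocol section 4) and 90 or more days (SAP monthly report template).

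**The concern.** The study's main product is the share of women at each step of the PrEP cascade, so the denominator defines the result. Two analysts following different sections could report different continuation figures from the same data, and the choice could be made after the data are seen.

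The completer rule is also a poor choice in itself. Under the missed-visit definition, staying in follow-up and continuing overlap, so selecting completers selects partly on the outcome. If women who leave follow-up continue PrEP less often, the completer figure is the flattering one.

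The same sentence reaches the HIV outcomes. Protocol section 4 lists seroconversion as a reason for censoring, and the laboratory section removes seroconverted women from the rest of the study. A woman who seroconverts before the last visit therefore cannot be a completer, and a literal reading would drop her from the count of maternal HIV acquisitions.

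**Working it through.** **Inputs (SAP 2.2 and the sample size text).** 1200 enrolled; 60% initiate; 75% of those on PrEP continue at 12 months; 70% of those retained adhere.

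**Reproducing the plan's counts.**

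- 1200 × 0.60 = 720 initiators
- 720 × 0.75 = 540 retained, so 720 − 540 = 180 not retained
- 540 × 0.70 = 378 adherent

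All match the documents. The planned 75% is 540/720, so it has all initiators in the denominator.

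**Completer denominator.** Let g be the share of the 540 retained women who complete 12 months postpartum, and f the share of the 180 non-retained women who do. The documents give neither, so both are assumptions. Retention at 12 months stands in for retention at 12 months postpartum.

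Continuation among completers = 540g / (540g + 180f)

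| g | f | Calculation | Continuation |
|---|---|---|---|
| 1 | 1 | 540/720 | 75.0% |
| 1 | 0.75 | 540/675 | 80.0% |
| 1 | 0.50 | 540/630 | 85.7% |
| 1 | 0.25 | 540/585 | 92.3% |
| 0.9 | 0.9 | 486/648 | 75.0% |
| 0.9 | 1 | 486/666 | 73.0% |

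The bias is upward if g > f, zero if g = f and downward if g < f.

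**If the sentence covers only the relative-risk comparisons.** The women without continuation who remain for predictor models number 180f: 135, 90 or 45 at f = 0.75, 0.50 or 0.25, against 180 among all initiators.

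**Active cohort.** The text does not say whether women censored for seroconversion, moving, transfer or loss leave it, or on what date it is counted. If they leave it, the proportion has the same selection problem, by an amount the documents do not fix.

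**The case against.** The best defence is context. The sentence always stands directly before the relative-risk and alpha sentence, twice under sample size and once beside unfilled template instructions. It may be copied text meant only for the association models. The named primary description is cumulative incidence with product-limit graphs, which ordinarily keeps women until censoring, and the continuation shell is headed by women on PrEP. The SAP also plans inverse probability of censoring weighting and multiple imputation.

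Much of this stands, and it makes a completer headline less likely. It does not settle the question. The text never limits the sentence, and in SAP 2.4 it sits inside the primary analysis. Table 1 still defines a proportion over an undefined cohort. Weighting is offered as a further bias analysis alongside complete-case analyses, and imputation as subsidiary; neither names the headline population. Even on the narrow reading, women lost early would leave the predictor models, although the SAP itself calls such losses highly informative about later steps.

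Three stronger readings are tempting and not supported:

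- **That following women until censorship (Protocol section 4) contradicts the completer rule.** That passage describes follow-up, not an analysis set.
- **That the plan ignores withdrawal.** SAP 2.2 item 6 says exclusions for withdrawal and missing data will be considered.
- **That a completer set would leave the initiation comparison underpowered.** The plan states that "A sample size of 1200 women yields 80% power to detect identify a relative risk of 2.0 or greater". With 720 women, 60% initiating and a relative risk of 2.0 for initiation or non-initiation, power is at least 96% for every feasible exposure share tried from 5% to 90% (shares assumed).

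**Conclusion.** The concern holds in this form: an unrestricted completer sentence conflicts with the all-initiator populations for persistence and time to non-continuation, does not fit the primary description or the continuation shell, and stands beside an undefined active cohort. The headline continuation denominator is therefore open. This should be fixed before analysis.

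The size is illustrative. From a planned 75%, the completer figure is 80%, 86% or 92% if 75%, 50% or 25% of the 180 non-retained women complete and all 540 retained women do. A reader might infer that continuation must be inflated, or would reach 100%. The documents do not support that: they give no completion shares, the bias vanishes when both groups complete equally and reverses when the non-retained complete more often, and 100% needs none of the 180 to complete. The effect is also less mechanical under the 45-day refill definition.

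The conflict in wording is certain. Which population the authors intended is not.

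**What to change.** Delete the completer sentence in all three places, or limit it to a labelled sensitivity analysis. Replace the active cohort with fixed denominators:

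- **Initiation:** all enrolled women.
- **Continuation:** all women who initiated PrEP.
- **Objective persistence:** all initiators with a dried blood spot due at each time point, with the planned weighting and imputation for missing values.
- **HIV incidence:** all enrolled women, with person-time up to seroconversion and the seroconversion counted.

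Name one headline continuation estimate: the proportion of all initiators, with loss to follow-up counted as non-continuation. Women who move, transfer or seroconvert stay in the denominator, count as not continuing, and are shown in separate rows. Label the product-limit analysis that censors those women as supporting.

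So that these denominators can be applied, reconcile the two continuation definitions, say which is primary, and reconcile the two loss-to-follow-up rules.

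The cost is protocol and SAP wording and a little more analysis work, with no new data collection. Reported continuation may be less favourable than a completers-only figure.

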## **2.5. Secondary analyses**

**Purpose:**

- (1) To evaluate prevention-effective measures of PrEP continuation and persistence during periods of sexual activity/risk
- (2) To evaluate patient and provider-level factors associated with the PrEP cascade using quantitative and qualitative approaches

**Methods/Approach:**

See **Table 1** for precise definitions of prevention effective PrEP continuation and persistence

- (1) *Secondary analysis:* Describe each outcome listed above via cumulative incidences at fixed intervals (e.g., cumulative PrEP continuation after 1 year in study) and incidence densities over time. The general statistical approaches to these outcomes are analogous to the primary outcomes (above). Data will be described graphically, including product-limit graphs, with preliminary analyses based on standard approaches for rates and proportions.
- (2) Other analysis approaches on the PrEP cascade:
  - a. When time-dependent or visit-specific covariates are included in the analysis of cumulative PrEP initiation we will shift to a mixed-effects setting with random effects around individual participants.

Other outcomes (secondary outcomes):

- a. **Predictors of attrition at key steps in the PrEP cascade:** Methods will involve mixed methods analysis. Utilizing the qualitative data from the IDIs at month 7 and 12 of the study from a random selection of 60 participants (30 randomly selected from those who initiated PrEP and 30 randomly selected from those who chose not to initiate) to complement the quantitative data to understand factors associated with PrEP persistence and non-persistence, including 1) individual factors, (including risk perception, sexual activity and risk, substance use, and partner/family/community discouragement), 2) the pill regimen (side effects and concerns about adverse pregnancy or infant outcomes) AND patient-provider relationship and 3) the disease-related factors (including reasons behind stigma associated with PrEP taking).
  - i. **Individual factors:** Collected from CRFs in all participants (regardless of PrEP uptake) including: risk perception, sexual activity and risk, substance use, partner/family/community discouragement, sociodemographic variables, relationship characteristics and fear about adverse pregnancy and/or infant health outcomes. Collected from the sub-set of women participating in the IDIs.
  - ii. **Pill/study factors:** Collected from CRFs in participants who decide to take PrEP, including: side effects on PrEP, and barriers to attending frequent study visits and DBS during those visits, and provider participant communication and support

(measured from participant perspective). Collected from the sub-set of women participating in the IDIs.

- iii. **Disease-specific factors:** Collected from CRFs (in all participants, not just those who decide to take PrEP) on partner's HIV status (including knowledge of serostatus and uptake of couples testing and counseling), perceived risk of HIV exposure and acquisition, perceptions of PrEP efficacy, and stigma associated with PrEP and HIV. Collected from the sub-set of women participating in the IDIs.
- b. **HIV outcomes:** Describe the frequency of HIV outcomes, including maternal and infant incident HIV. Analyses will include pure-count and person-time approaches. While we expect the frequency of adverse HIV-related outcomes to be low, we will describe characteristics of women who did/did not acquire HIV, and consider further analyses using the approaches outlined.

## **2.6. Adverse effects**

***Purpose:***

To summarize and describe adverse intervention effects.

***Methods/Approach:***

Tabulation of adverse effects with each treatment group:

- (1) Number of events by type of event
  - Describe the frequency of any laboratory or self-reported side effects (e.g. changes in creatinine clearance, or self-reported side-effects [GI symptoms, headache, and etc]). Analyses will include pure-count and person-time approaches. Confidence intervals will be calculated following the method of Breslow and Day. We will also describe pregnancy (miscarriage, stillbirth) and infant outcomes over time (including birthweight, gestational age at delivery, pregnancy loss) by PrEP status (on/off PrEP and by persistence to PrEP)
- (2) Number of subjects by highest grade of event
- (3) Reasons for termination of treatment

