**Step 4:** *For participants on PrEP*, the study nurse performs a blood draw for creatinine clearance and a finger prick for DBS testing for adherence measures and (if applicable for this visit). See Table 1 for study calendar.

**Step 5 (for women on PrEP):** At each visit the study counselor will ask, and record responses, all participants on PrEP about any side effects associated with TDF/FTC, including diarrhea, nausea, fatigue, headache and rash (which are seen in about 10% of participants during the initiation of therapy). We will encourage participants to contact the study nurse if they experience side effects between visits.

**PrEP retention methods to improve adherence:** Each study visit will include counselling from peer counsellors who will discuss the importance of retention and adherence to PrEP for effectiveness. We will adapt messages from ongoing PrEP studies conducted by co-I [name] and team. We will also provide participants with a brochure to take home that discusses retention, adherence and side effects of PrEP. Each visit will include group and individual counselling. Group counselling will be led by a mother who has successfully taken PrEP for 3+ months to guide a discussion about the importance of retention, reminders on how to take the medication daily and how to address side-effects (e.g. nausea, headaches, etc).

**Step 6:** PrEP provision (for 1 or 2 months) and appointment reminder

*Follow-up & retention:* Tracing information will be taken at the enrolment visit and updated at each study visit. Retention activities will focus on scheduled measurement visits. Following our established approach in this

setting, we will provide reminder calls to participants before their measurement visits, and initiate tracing, including home visits, for women who do not attend the measurement visit within one week of the scheduled visit.

*PrEP provision:* monthly for the first 3 months, and then 2-months intervals after that. Participants on PrEP will have regular monitoring with laboratory tests, including creatinine levels to check for changes in renal function and dried blood spots (DBS) for adherence measures. Those with HBsAg+ will be excluded from the study. We will test for HIV seroconversion at every study visit.

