- **Measurement of use of PrEP:** Conducted through alternate definitions of the main outcomes (e.g. persistence by self-report versus persistence by pharmacy refill), compared using measures of agreement and will be analyzed as independent models to contrast estimated associations.
- **Measurement of prevention-effective execution:** Execution refers to PrEP persistence during a time when at-risk sex happens. It is calculated by: number of doses reported, or recorded/number of expected doses based on HIV risk and PrEP initiation/discontinuation
- **Prevention-effective continuation:** Prevention-effective continuation describes the duration of PrEP use during periods of HIV risk and references the absolute time of use during pregnancy and breastfeeding periods. We will adapt the methodology from previous PrEP studies in SA including FEM-PrEP to create a semi-ordinal composite persistence score from blood specimens from DBS every 2-months.  
For *Aim 1*, each outcome will be described via cumulative incidences at fixed intervals (e.g., cumulative PrEP initiation by delivery) and incidence densities over time. The general statistical approaches to these outcomes are analogous; data will be described graphically, including product-limit graphs, with preliminary analyses based on standard approaches for rates and proportions.

For *Aim 1*, we will also describe the frequency of HIV outcomes, including maternal HIV acquisition and MTCT, and any laboratory or self-reported side effects (e.g. changes in creatinine or self-reported side-effects [GI symptoms, headache, and etc.]). Analyses will include pure-count and person-time approaches; for the latter, confidence intervals will be calculated following the method of Breslow and Day. We will also describe infant outcomes over time (including birthweight, gestational age at delivery, pregnancy loss and any infant illness, hospitalization or death). While we expect the frequency of adverse HIV-related outcomes to be low, we will

describe characteristics of women who did/did not acquire HIV, and consider further analyses using the approaches outlined above.

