To address *Aims 1 and 2*, the modelling approach will vary depending on the nature of the outcome. PrEP initiation will be modelled using a probit model (preferred to estimate risk factors for common outcomes) with individual-level covariates as fixed effects; when time-dependent or visit-specific covariates are included in the analysis of cumulative initiation (for *Aim 2*) we will shift to a mixed-effects setting with random effects around individual participants. PrEP continuation will be examined using similar approaches; in addition, we will use time-to-event methods to estimate factors associated with time to loss (non-continuation) among women having initiated PrEP. PrEP persistence will be modelled using mixed effects probit models as above and generalized estimating equations to examine the marginal effect of individual-level covariates on persistence during the study. Throughout, robust estimates of standard errors will be used.

For each outcome, covariates in the multivariable models will be selected a priori using directed acyclic graphs; the main exposures of interest include: age (<25 vs. >25 years old), pregnancy status (by trimester and pregnant vs. postpartum), relationship status (married/cohabiting vs. not) and substance use (vs. none). We will explore associations within subgroups of participants using interaction terms in predicting outcomes involving these four covariates in particular. Throughout the analysis of outcomes in the PrEP cascade, losses of patients at early stages are highly informative about outcomes later in the cascade. To specifically address this, we will perform further bias analyses with inverse probability of censoring weighting in addition to complete case analyses. We will also use multiple imputation via chained equations for missing data [83] to examine the potential impact of missing data.

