#### Adverse events and serious adverse events (PrEP use defined as taking PrEP in last 30 days)

	PrEP users (N)	%	PrEP non-users (N)	%	Comment
Adverse event reported (n=# of events and # of participants)					
Type of events					
Serious adverse event reported (n= # of events)		% over # of participants in study			
Type of events					
HIV testing					

HIV ab+					
HIV ag+					
HIV ag/ab+					

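### Side-effect event rates get Poisson-type person-time intervals, which will be too narrow if repeat reports by the same woman are counted

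*Combined protocol and SAP*

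**What the plan says.** SAP 2.6 (Adverse effects) has three numbered items. The first is "Number of events by type of event". Under it come laboratory and self-reported side effects, with the instruction: "Analyses will include pure-count and person-time approaches. Confidence intervals will be calculated following the method of Breslow and Day". The second item is a separate woman-level count, "Number of subjects by highest grade of event".

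SAP section 1 (analysis considerations for Aims 1 and 2) and protocol section 6 limit the interval method to the person-time analyses: "for the latter, confidence intervals will be calculated following the method of Breslow and Day".

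Ascertainment is repeated. Protocol section 5, Step 5 of the follow-up visits, states: "At each visit the study counselor will ask, and record responses, all participants on PrEP about any side effects associated with TDF/FTC". The shell for adverse events in SAP section 4 also keeps the two units apart: "Adverse event reported (n=# of events and # of participants".

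No section says whether the numerator of the rate is every report, each distinct episode, or the first event per woman. None says whether a symptom present at two successive visits is one event or two.

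**The concern.** A Poisson interval for a rate takes the variance of the event count to equal its mean. If some women report nausea at several visits and most never do, the count varies more than that and the interval understates the uncertainty. The SAP deals with within-woman correlation for persistence, through mixed models and generalized estimating equations, but names only Breslow-Day for the side-effect rates.

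What is at stake is how precise the tolerability rates appear. SAP Table 1 lists side effects and adverse events as a secondary outcome to be compared by PrEP use. A reader who sets two such rates side by side with intervals that are too tight could take clustering within a few women for a real difference.

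**Working it through.** The plan states no side-effect rate, event count or interval, so there is no figure of its own to reproduce. As an input check, the SAP 2.2 chain holds: 1200 × 0.60 = 720, × 0.75 = 540, × 0.70 = 378.

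**Inputs from the documents**
- Women on PrEP: 720 (SAP 2.2: "Estimated that 60% of women (n=720) will initiate PrEP during the study period").
- Follow-up: mean 18 months, taken as 1.5 years each.
- Visits: at most 7 (months 1, 3, 6, 9, 12, 15 and 18 in the continuation shell, SAP section 4).
- Symptom frequency: about 10%, which the protocol gives for the start of therapy.

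**Assumptions**
- Breslow-Day is taken as exact Poisson limits on the event count divided by woman-time; the plan prints no formula.
- The level is 95%, as in another SAP shell; SAP 2.6 gives none.
- The 10% is used as a constant per-visit report probability, with all 7 visits attended and 1.5 years on PrEP.
- The within-woman correlation (ICC) is not given and is varied from 0 to 0.5.

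**Base case.** Events = 720 × 7 × 0.10 = 504. Woman-years = 720 × 1.5 = 1,080. Rate = 504/1,080 = 0.467 per woman-year. The Poisson 95% interval is 0.427 to 0.509.

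**Effect of repeat reports.** With m visits and report probability p:

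true variance / Poisson variance = (1 − p)[1 + (m − 1) ICC]

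At p = 0.10 and m = 7, this is 0.9 × 1.6 = 1.44 at ICC 0.1, 0.9 × 2.8 = 2.52 at ICC 0.3 and 0.9 × 4 = 3.60 at ICC 0.5. The ratio passes 1 at ICC = (1/0.9 − 1)/6 = 0.019. Beta-binomial simulation (4,000 runs per setting, 720 women, 7 visits) gave:

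| ICC | Coverage, Poisson interval | Coverage, per-woman robust interval | Robust width / Poisson width |
|---|---|---|---|
| 0 | 96.6% | 95.0% | 0.94 |
| 0.05 | 93.3% | 94.9% | 1.07 |
| 0.1 | 90.1% | 95.1% | 1.19 |
| 0.3 | 79.9% | 95.5% | 1.57 |
| 0.5 | 69.8% | 94.5% | 1.87 |

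With 4 visits instead of 7, the formula (coverage = 2Φ(1.96/√ratio) − 1) gives ratios of 1.17, 1.71 and 2.25 at ICC 0.1, 0.3 and 0.5, and coverage of 93.0%, 86.6% and 80.9%. With reports concentrated at the first visit (0.10, then 0.02 per visit) and ICC 0.1, simulated coverage is 90.7%.

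**A second model.** Let 10% of women ever be symptomatic, each making 1 + Poisson(k − 1) reports, with mean k. Then

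variance ratio = [0.1((k − 1) + k²) − (0.1k)²] / (0.1k)

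- k = 1: (0.1 − 0.01)/0.1 = 0.90, slightly conservative.
- k = 1.5: (0.275 − 0.0225)/0.15 = 1.68, coverage about 87%.
- k = 2: (0.5 − 0.04)/0.2 = 2.30, coverage about 80% to 82%, depending on the form of Poisson limits used.

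**Does another sentence cover these rates?** "Throughout, robust estimates of standard errors will be used" closes the paragraph on the probit, mixed-effects, estimating-equation and time-to-event models for initiation, continuation and persistence. The side-effect rates are described elsewhere, with their own named interval, so this sentence does not clearly reach them.

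**The case against.** The best defence is that the premise is not written down. A count of events by type could mean first events only, in which case no clustering arises. With no within-woman correlation the Poisson interval is slightly wide (96.6% coverage). The 10% figure belongs to the start of therapy, and protocol section 1 says the early symptoms fade over a few weeks. With visits months apart, many women would report a given symptom about once. The 10% also pools several symptoms, while the counts are by type, so only repeats of the same symptom inflate a given rate. Women who stop PrEP because of side effects add fewer repeats. Woman-level summaries are already planned and are immune to the problem.

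Much of this stands. It rules out stating as fact that the intervals are too narrow, and it makes the high correlations, or several reports per symptomatic woman, the upper part of the range. A reader might also infer that misleading intervals will reach the DSMB or produce false differences by PrEP status. The documents do not support that: the adverse-event shell and the monthly and quarterly templates show counts and percentages without these intervals, and no test or decision rule is attached to the side-effect comparison.

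The defence does not remove the natural reading. Listing events and subjects as separate items makes most sense if a woman can contribute more than one event, and no first-event rule is given.

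**Conclusion.** The point holds conditionally. If more than one report of the same event type by a woman enters the numerator, the planned intervals ignore within-woman correlation and will be too narrow once that correlation exceeds about 0.02 (7 visits, 10% per visit). At modest correlation (0.1) the loss is about five points of coverage. It reaches 15 to 25 points only at correlations of 0.3 to 0.5, which the documents neither support nor exclude. The correlation, the constant 10% per visit, full attendance and full time on PrEP are all assumptions.

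The scope is narrow: secondary, descriptive rates of recurrent side effects. HIV acquisition, pregnancy loss, the subject-level tables and the primary cascade outcomes are not affected. It is still worth correcting, because the named method does not suit the counts it is most naturally applied to.

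**What to change.** Amend SAP section 1 and SAP 2.6, and align protocol section 6:

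1. Keep Breslow-Day or exact Poisson limits for events counted once per woman: HIV acquisition and the first occurrence of each side-effect type.
2. For recurrent counts, define the event and say how a symptom that continues across visits is counted. Give the rate with a variance clustered on the woman, from a Poisson estimating-equation model with robust standard errors or a bootstrap that resamples women.
3. For each event type, report the number of women with at least one event, with a binomial interval.

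The cost is a few lines of SAP text and code. The intervals for recurrent events become somewhat wider: about 1.2 times at a correlation of 0.1 and 1.6 times at 0.3 in the 7-visit illustration.
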